- Participants with applicable smart phones may have CLARITY® push notifications on the CLARITY® mobile app about weekly time in range comparison enabled during the study.

- For app users, the “Share and Follow” functionality will be discussed and encouraged (i.e. the study participants are able to invite followers to review their glucose levels).

- For participants using the receiver only, the receiver will be downloaded into the CLARITY® clinic account at each visit. CGM data and reports. RT CGM-Participants will also keep a logbook of their blood sugars for their provider to review.

Control Group

The participants of the control group will perform self-monitored blood glucose testing with a study-provided blood glucose meter, including testing supplies. They will perform capillary blood glucose monitoring as routinely used for patients with GDM, i.e., at least four capillary blood glucose values daily including measurements in a fasting state as well as 1h after starting each meal. The study participants will keep a logbook of their glucose values

Each participant of the control group will be assigned a study blood glucose meter to measure and store their blood glucose values during the study.. A commercially available desktop software used in conjunction with the glucose meter for blood glucose monitoring will be utilized for downloading the meter data at each visit ensuring that dates and times are correct. Blood glucose meters used by the control group will be assessed to establish frequency of testing (overall and per week) as well as percentage of days with less than four measurements per day.

Subjects who got randomized to the control group then decided to withdraw from the study and discontinue their participating in the study will receive an email asking them to fill out a survey questionnaire to explain the main reason and any other reasons for withdrawal from the study. The survey will be sent to subjects’ email through a link from Redcap and it won’t take more than 10 minutes to complete.

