Glucose Meter: A glucometer is a device for measuring the concentration of glucose in the blood by placing a small drop of blood on a disposable test strip where a chemical reaction with glucose alters the electrical conductivity of the strip. It records glucose and also records average glucose and standard deviation and goal range can be set and show time in range. This is standard of care for patients with gestational diabetes in pregnancy to check fasting and 1 or 2 hours post-meals.

Gestational DM Nutritional Classes:

As per local standard of care, nutritional counseling for GDM is provided to all patients with diagnosis of GDM and all participants will be offered and asked to complete this session. Completion of session will be assessed at visit 2.

RT-CGM Handout:

A simple educational handout has been developed to explain glucose goals in pregnancy and also how food and activity affects blood sugars. This handout will be reviewed with RT-CGM participants at visit 0 and adapted to fingersticks as well for the control group (see Appendix A1, A2)

K .Measurements (Appendix C): We will measure HbA1c and fructosamine at the beginning of the study period and HbA1C at 30-32 and HbA1C and fructoasmine at 34-36 weeks. At each visit, blood pressure, maternal resting heart rate, maternal weight and height will be measured. At baseline and 34-36 weeks,

questionnaires on diet and physical activity and personal wellness questionnaires will be obtained. In the intervention group at 34-36 weeks, a questionnaire about CGM technology and perception of benefit of CGM use will be obtained.

Anthropometrics: Height will be recorded in centimeters and inches by a stadiometer. Weight will be recorded in pounds and kilograms using a Digital scale. Two measurements will be taken, and the average will be used. **Blood pressure and pulse** are taken with an Professional Digital blood pressure machine. Two measurements will be obtained at each appointment. If performed via remote televisit then patients will use their own blood pressure cuff and available scale.

L. Collection of Human Biological Specimens:

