There is the possibility of bruising, soreness and infection at the sites of needle sticks for blood draws, finger sticks for checking glucose levels and at the insertion sites of the CGM device. All participants will be provided with an emergency number for who to contact if any problems arise.

Continuous Glucose Monitoring Device: Participants may have temporary discomfort at the time of inserting the small filament. This can include bruising or redness of the skin, rare allergy to tape used to keep the device in place, infection at the insertion site, and potential perceived dislike of having a medical device on them for 10 days.

There is the risk of lightheadedness, dizziness and fainting from having blood drawn.

There is the possibility of potential embarrassment answering questionnaires. Participants are told they can leave questions blank if they are uncomfortable answering them.

There is the risk of anxiety because the medical history contains some sensitive questions like alcohol and drug history and questions about previous pregnancies.

There may be confusion about when to test blood sugar which could cause anxiety. Participants will be told to follow the instructions of their provider. Participants will be provided with study contacts for any questions and the study will work in conjunction with the participants' OB provider about blood sugar testing instructions.

There is the risk for participants in RT-CGM in the intervention group missing alerts if the alert notification is turned off.

There is the risk of lack of accuracy of the CGM read outs in the intervention group if the participant takes acetaminophen.

There is the risk for both groups if during insertion of the CGM the insertion wire breaks and becomes lodged under the skin and requires removal.

There are some skin issues that can occur when using the CGM device such as allergic reactions to the device that are localized and can include bruising, rash, soreness, and infection. This skin reaction can also be caused by the tape used to secure the device.

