There is the risk of suicidal ideation presenting itself while answer the PHQ-9 questionnaire. If the subject endorses suicidal ideation answering the PHQ-9 our plan will be to call the participant immediately and discuss the participant's answer, provide the participant the number for a suicide hotline, and to call the PI if the participant endorses the intent to hurt themselves. The PI of the study will be notified immediately and will make the decision to call 911.

We will be checking for completion of the questionnaires after links to participants are sent to them and the PHQ-9 answers will be checked at that time. Our time frame for checking the PHQ-9's completion is within 3-5 days after being sent out. Our plan will be put into action if any questions are answered in a manner concerning to our study personnel who will be trained for our action plan and what to watch for within an hour of seeing the answer to the question

Body measurements: Participants may experience discomfort or embarrassment associated with weight and fundus measurements.

Q. Benefits:

Participants may receive some benefit for glucose control in pregnancy with RT-CGM which may or may not translate to improved fetal and maternal outcomes. Control patients will likely receive no benefit from blinded CGM and fingersticks 4 times a day fasting and post-meals as these are the current standard of care in GDM. This research may benefit society by enhancing our understanding of medical devices use in GDM and thus help establish new procedures and practices that are associated with GDM.

R. Conflicts Of Interest:

No conflicts of interest are noted.

S. Confidentiality:

All of the subjects' personal information, clinical data and consent documents will be stored in a secure location in a locked file cabinet in the University of Washington OB research coordinator's office. The subjects' personal information and research related clinical data other than routine laboratory results will be accessible only to the Principal Investigator and the research staff associated with the study. Organizations that may

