inspect and copy the participant information include the IRB of the University of Washington. A master code linking the unique study numbers with subjects' identifying information will be kept by the Principal Investigator or by the Project Officer in a locked file cabinet. Additionally, all data collected by coordinators will be entered and managed through the encrypted Research Electronic Data Capture (REDCap) system maintained at University of Washington. All data is de-identified with no personal health information entered (PHI). REDCap was developed specifically around HIPAA security guidelines. REDCap has been disseminated for local use at more than 940 other academic/non-profit consortium partners in 75 countries. REDCap servers are housed in a local data center at CNMC, and all web-based information transmission is encrypted. This system is accessed through a secure login and password. Only the RedCap database coordinators and study staff will have access privileges to the University of Washington data set and will be strictly prohibited from sharing passwords. All will undergo the standardized authorized training provided by the REDCap team. Staff will maintain files in password-protected documents on HIPAA-compliant servers. REDCap programmers build in quality controls for the data that will be collected according to their stringent protocols. Data will be stored for 3 years after study completion for possible re-analysis and sub-group analysis that the clinical team may determine to be useful. More information about the consortium and system security can be found at <http://www.projectredcap.org>. [name] and her research team will destroy the informed consent, research source documents, data files, and master code 3 years after the completion of the study. This will allow time for the PI and collaborators to reexamine the data as needed in the revision process for manuscripts submitted to peer-reviewed journals.

All information that the study subjects provide study personnel is for research purposes only and, as such, names and any other identifying information will not be reported or published in papers, presentations, or proposals that result from this research.

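### Section P times PHQ-9 review from sending the link, so a suicidal-ideation answer may wait up to 5 days, and forms completed after day 5 have no review deadline

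*Combined protocol and SAP*

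**What the plan says.** Section P names suicidal ideation as a risk of giving the PHQ-9. Questionnaires go to participants as links. Staff look to see whether they have been completed, and "the PHQ-9 answers will be checked at that time". The timing is stated once: "Our time frame for checking the PHQ-9's completion is within 3-5 days after being sent out". If an answer is concerning, trained staff start the action plan "within an hour of seeing the answer to the question". They telephone the participant, talk through her answer and "provide the participant the number for a suicide hotline". The principal investigator is informed at once and decides whether to call emergency services.

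Earlier in the same section there is a general safeguard: "All participants will be provided with an emergency number for who to contact if any problems arise". Section H (Study Design) adds that routine obstetric care continues between visits.

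The list in Section U includes a Suicide Plan (Appendix W), a Data and Safety Monitoring Plan (Appendix T), the PHQ-9 form and the consent form. Their text was not available for this review.

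**The concern.** The response in Section P is meant to be quick: an immediate call, immediate notice to the principal investigator, and an hour as the outer limit. All of it, however, depends on staff having read the form. The step before that is timed in days, from an event (sending the link) that has no connection with when the woman answers. Staff could follow the main text exactly and still first learn of an endorsed suicidal-ideation item several days after it was submitted.

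The trial itself asks the question that reveals the risk, so the interval between her answer and someone reading it is under the trial's control. What is at stake is participant safety. Sample size, power and the analysis are not affected.

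**Working it through.** No statistical formula applies. The check is timeline arithmetic on the rules in Section P.

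**Inputs**
- Link sent on day 0 (the reference point in Section P).
- Completion check, at which answers are read: 3 to 5 days after sending, so day 5 is the outer limit. An earlier check is compatible with the wording.
- Action: at most 1 hour after staff see the answer.
- Assumption: days are calendar days of 24 hours. The text does not say otherwise.

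**Formula**

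Delay from submission to the end of the action hour = (day of check − day of completion) × 24 h + 1 h.

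**Under the current main text**

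| Completed | Read on | Delay |
|---|---|---|
| Day 0 | Day 0 | 0 × 24 + 1 = 1 h |
| Day 0 | Day 3 | 3 × 24 + 1 = 73 h |
| Day 0 | Day 4 | 4 × 24 + 1 = 97 h |
| Day 0 | Day 5 | 5 × 24 + 1 = 121 h |
| Day 2 | Day 3 | 1 × 24 + 1 = 25 h |
| Day 2 | Day 4 | 2 × 24 + 1 = 49 h |
| Day 2 | Day 5 | 3 × 24 + 1 = 73 h |
| After day 5 | not stated | no limit stated |

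The longest delay that complies with the main text, for a form completed by day 5, is 121 h. It falls on the woman who answers most promptly. Once day 5 has passed, the main text gives no date by which a newly completed form must be read.

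**Under a check every working day until completion** (form submitted just after a check)
- Between consecutive working days: 24 + 1 = 25 h.
- Friday to Monday: 72 + 1 = 73 h.
- Over a three-day weekend: 96 + 1 = 97 h.

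These limits apply whenever the form is completed, so they also cover late forms.

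**What cannot be computed.** The documents give no completion times and no endorsement rate, so no typical delay follows. The number of forms is not fixed either. Section K says that at baseline and 34-36 weeks "questionnaires on diet and physical activity and personal wellness questionnaires will be obtained", but does not name the PHQ-9, and the Visit 3 list in Section H does not mention it. Section H also places questionnaires within the week 0 session, where staff may see them sooner.

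**The case against.** The strongest objection is that the controlling document is unseen. A dedicated Suicide Plan is where review intervals, alerts and repeat checks would be expected, and Section P may only summarise it. A faster rule there would also comply with the 3 to 5 day limit. This stands as a limit on the conclusion: from the text available, a true gap cannot be told apart from a main text that lags behind its appendix. It does not remove the point, because Section P states a rule that staff could follow as written, and it would need aligning in either case.

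A second objection is that the wording may describe continuing checks, with 3 to 5 days as an outer limit. That is a fair reading. A reader might infer that there is exactly one check and that a late form is never read; the documents do not say so. What can be said is that earlier or repeated checks are allowed but not required, and that no deadline is given after day 5.

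Third, the plan has real safeguards: trained staff, the call, escalation, the general emergency number and routine obstetric care. They deserve credit, but none of them makes staff read the form sooner. A reader might go further and infer that the hotline number is withheld until the call. Section P shows only that it is given in the call. The consent form or the PHQ-9 form may already carry it.

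Fourth, the documents contain no standard that 3 to 5 days fails, and the working-day check still leaves 73 h over a weekend and 97 h over a long weekend, the same as reading a day 0 form on day 3 or day 4 now. Both statements are correct. The gain is on ordinary weekdays and for late forms, and the acceptable maximum is for the investigator and the IRB to set.

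**Conclusion.** The point holds as a statement about the main text. Section P counts PHQ-9 review from the day of sending and counts the action hour from when staff see the answer. A form completed on the day of sending may wait up to 5 days, or 121 h including the action hour, and no review deadline is stated for a form completed after day 5.

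This rests on reading the days as calendar days, and on the main text alone. Appendix W, Appendix T, the PHQ-9 form and the consent form may already require faster review or supply crisis numbers. The figure of 121 h is what the text permits, not an expected delay. A reader might infer that many women are exposed to it, but the documents do not allow any count of forms or women affected.

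The point is best treated as a cheap improvement to participant safety.

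**What to change.** 1. **Time the review from submission.** If the survey platform supports it, send an automatic alert on the suicidal-ideation item to the staff already trained for the action plan. Section P does not name the platform. The withdrawal survey in Section J goes out by "email through a link from Redcap", so assuming the same system is reasonable, but it should be confirmed. Otherwise, check every working day until the form is completed. The investigator and the IRB should set the maximum time and decide whether to provide evening and weekend cover.
2. **Show the hotline and emergency numbers with the PHQ-9** if they are not already there, so that they do not depend on a staff call.
3. **Align Section P with Appendix W.** If Appendix W already sets faster review, this step alone settles the review time.

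The cost is one protocol paragraph, a small set-up effort for the on-screen numbers and any alert, and somewhat more frequent checking by existing staff. No visits or assessments are added. The drawback of the working-day check is the weekend and long-weekend delay shown above, unless cover is arranged.

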pregnancy obstetric provider. The intervention group will continue the RT-CGM device and will be instructed to continue fingersticks only when concerned for hypoglycemia and/or inaccuracy of sensor. The control and intervention groups will follow-up serially for the duration of pregnancy (see schematic for visits below). The control group will wear the blinded CGM at serial timepoints throughout pregnancy and the intervention group will have serial download of RT-CGM. Participants will also have labs checked every 8 weeks which will include HbA1C and fructosamine at beginning and end of the study. It is estimated that participants will be enrolled at 24-28 weeks and have 4 visits (estimating a pregnancy duration of 40 weeks). Some participants may receive a diagnosis of gestational diabetes earlier and thus have more sessions. Maternal and neonatal outcomes will be abstracted from delivery records.

[figure not shown]

Figure 1: Study Design Schematic: N=100 Control N=50 GDM Intevention: GDM N=50

*Approximate Total duration of CGM use would be 14-22

**see timeline for measures appendix B

Figure 2: Timeline for Visits Based on High Risk for Gestational Diabetes and Typical Risk

		Screening Visit 0	Visit 1b High risk	Visit 1a	Visit 2++	Visit 3	Visit 4*
Gestational age Intervention	High Risk	14	20-22 weeks	24-30 weeks	30-32 weeks	34-36 weeks	38-40 Weeks

Gestational age Intervention	Typical Risk	24-28	N/A	24-30 weeks	30-32 weeks	34-36	38-40 Weeks
Gestational age Control	High Risk	14	14-16 weeks	24-30 weeks	30-32	34-36	38-40 Weeks
Gestational age Control	Typical Risk	24-28	N/A	24-30 weeks	30-32 weeks	34-36	38-40 weeks

+++ visits will be a minimum of 2 weeks apart

*38-40 week data only collected in participants that make it to 38- 40 week gestational age

Screening/Pre-Intervention Visit(week 0):

Consent (appendix R) will be obtained prior to any screening procedures being completed, and conducted in a quiet room or private televisit. Participant will be given ample time to ask questions, and a copy of the signed consent form will be given prior to start of screening visit. Participants will fill out a contact form, including emergency contact. Study staff will review medical history and medications, pregnancy history, patient's mother's pregnancy history, sleep history, and lipid profile if available (appendix D), as well as all inclusion/exclusion criteria.

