RT-CGM and meter will be downloaded for the intervention group and meter downloaded for the control group. Vital signs, weight and medications and dose will be recorded at each visit and results of maternal ultrasound if available (appendix M).

Between Visits: In the weeks between visits participants will continue their routine OB care with their OB providers. The OB providers may or may not be aware that their patient is participating in the study or have knowledge of their study group allocation. The participants will provide their OB providers the usual blood sugar values that they typically supply to their OB provider. For the control group this will be fingerstick glucose values for fasting and 1-hr post-meals. For the intervention group, this will be a log of the CGM

glucose values at the time of fasting and 1-hr post-meals. The OB providers will not be expected to use the CGM system itself.

Delivery: EMR will be reviewed for maternal and fetal outcomes.

I. Randomization/allotment: Randomization/allotment: Once they have signed the consent form, study participants will be randomized to treatment group. The project will use random, permuted blocks within strata to do this. Two participant factors will be considered in creating the strata: 1) weeks pregnant (14-24 weeks or 28 weeks); and 2) pre-pregnancy BMI (≤ 35 and >35). Thus, the strata will be:

Pregnant 14-24 weeks and BMI ≤ 35

Pregnant >24 weeks and BMI ≤ 35

Pregnant 14-24 weeks and BMI >35

Pregnant >24 weeks and BMI >35 .

Separate randomization lists will then be prepared for each of the above strata, using random permuted blocks generated in SAS 9.4. The lists will be transferred (by the statistician) to a sequence of sealed envelopes with the treatment group noted on a card within.

Since this is a small clinical trial, there is the potential problem of uneven distribution of study participants across the strata. However, we believe we have mitigated this potential by having only 4 strata. Also, this approach works better for this project than other approaches (such as the minimization method) due to the relatively greater level of staffing effort required for those approaches to work.

Source: Pocock SJ. 1983. Clinical Trials. A Practical Approach. Chichester, New York: John Wiley & Sons

J. Study Procedures, Materials and Devices :

Televisits:

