When the subject enrolls in the study, she will be assigned a unique study number that is not any part of her social security number or other personal identifier. These unique study numbers will be used to identify all information that subjects provide and any information that is collected from their medical records. The unique study numbers will be assigned sequentially according to the order of study enrollment and subjects will be identified by the initials of the group to which they are randomized and 3 numbers according to their entry into the study beginning with 001. Therefore, the first subject randomized to the DMC (control) group will be DMC-001 and the first subject randomized to the DMCGM (intervention) group will be DMCGM-001. A total of 50 DMC and 50 DMCGM subjects will be enrolled.

Although every precaution is being taken to protect participant privacy, breach of confidentiality is always possible. In the unlikely event of a breach of confidentiality, the nature of the research data is not of a sufficiently personal nature to negatively affect employment status, lead to civil/criminal liability, incur financial risks to the study participants, or other risks.

T. Subject Compensation:

Participants will be given \$50 after visit 0 and \$50 after visit 3. Visit 3 compensation will be given to participant upon return of blinded device or RT-CGM download at 34-36 weeks. If lack of CGM data necessitates unscheduled visits, the participant will receive an additional \$25 per visit up to a maximum of \$50 if 2 unscheduled visits are required. Subjects will also have use of the medical devices during the study for free: in the intervention group they will receive a glucose meter and test strips (total 50 test strips for free) to be used as needed. In the control group they will receive a glucose meter and 400 test strips for free if not covered by their insurance. No additional cost will be incurred by subjects.

If extra visits are necessary we will follow the OB clinic guidelines for COVID 19 screening. This money can be used for travel and parking but all study visits are piggy backed to a regular clinic visit so no extra travel or parking is required by the study although visits may be a little longer than usual

U. Appendix:

- A. Educational Material: Real-Time Continuous Glucose Monitoring educational material (A1) or Fingerstick educational material (A2)
- B. Table of Study Measurements
- C. Pre-Screening Checklist Telephone

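### Study IDs carry the treatment arm, so staff who abstract, enter or clean judgement-based delivery outcomes see the allocation even when they have no need to know it

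*Combined protocol and SAP*

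**What the plan says.** Section S (Confidentiality) sets the ID format: "subjects will be identified by the initials of the group to which they are randomized and 3 numbers according to their entry into the study". It gives one example per arm: "the first subject randomized to the DMC (control) group will be DMC-001" and "the first subject randomized to the DMCGM (intervention) group will be DMCGM-001". It then says what the ID labels: "These unique study numbers will be used to identify all information that subjects provide and any information that is collected from their medical records".

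Section H (Study Design) names the source of the delivery outcomes: "Maternal and neonatal outcomes will be abstracted from delivery records". The Delivery entry later in that section says "EMR will be reviewed for maternal and fetal outcomes". Neither place says who does this or whether that person is masked.

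Section S also has coordinators' data entered and managed in REDCap, with access for the database coordinators and study staff. It defines no masked role.

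**The concern.** Participants know which device they are using, and the obstetric provider may or may not know the allocation (Section H, Between Visits). Masking at abstraction and cleaning is therefore one of the few protections still available for the delivery outcomes, which serve Aim 2. Several of them have to be interpreted from narrative notes. An abstractor or data cleaner who sees the arm on the record may, without intending to, settle an ambiguous note differently in the two groups. The plan puts the arm there through a labelling convention that serves no analytic purpose. It reaches people who never met the participant as well as those who did.

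**Working it through.** No formula applies to the main point, so the check sets the relevant sections side by side.

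1. **Does the ID reveal the arm?** Yes. Under Section S the prefix is DMC for control and DMCGM for intervention, so the prefix alone gives the allocation.

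2. **Does that ID reach the delivery outcomes?** Yes. Section S applies it to "any information that is collected from their medical records". Section H obtains maternal and neonatal outcomes from delivery records and the EMR. Delivery outcomes are therefore filed under an ID that states the arm.

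3. **Does anything break the chain?** Nothing in the supplied text does. Throughout the protocol, blinding refers to CGM wear. No section provides for a masked abstractor, adjudicator or data cleaner. Section J mentions a sequential study number, allocated at randomization, for the CLARITY accounts, with no prefix mentioned; it is not said to replace the prefixed ID on chart data. Appendix B (table of measurements) and Appendix T (data and safety monitoring plan) are listed but were not available to check.

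4. **Who learns the arm only because of the ID?** Section J has the research coordinator insert the control-arm sensors, and Section H has device downloads that differ by arm at the visits. Staff doing that work know the arm whatever the ID says. REDCap database coordinators, data cleaners and any abstractor not involved in visits need not know it. For them the prefix makes unmasking certain.

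5. **Which outcomes are exposed?** Sorting the outcome lists in Sections O and K:
   - *Need judgement, with no operational definition given:* indication for induction or delivery, preeclampsia or gestational hypertension, respiratory distress, birth injury.
   - *Defined, but still dependent on the narrative:* shoulder dystocia.
   - *Little discretion:* gestational age, birth weight and the size categories derived from it, live birth or stillbirth, Apgar score, NICU stay, neonatal hypoglycemia (numeric thresholds), and HbA1c (a laboratory value).

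6. **Scale.** Sections D and S plan 50 women per arm. One event reclassified in one arm changes that arm's proportion by 1/50 = 0.02, or 2 percentage points. This shows how sensitive a proportion is at this sample size. It does not estimate bias, because the documents give no misclassification rate and no expected event rates for these outcomes.

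**The case against.** The strongest reply is that a neutral ID might mask nobody. This is a small study at one institution's clinics, coordinators collect the data, and no separate abstractor is named. If the staff who fit sensors and download devices also read the charts, they already know the arm. The chart may show it too, since intervention participants give their providers a log of CGM values. Most diagnoses are made by treating clinicians, so the abstractor largely transcribes. The sample size rests on HbA1c, and the hypothesis-testing models in Section E cover HbA1c, fructosamine, CGM readings and glycemic variability, not delivery outcomes. The protocol never promises masked abstraction.

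Much of this stands. It limits the gain and makes the point a design weakness rather than a contradiction. It does not explain why the arm should be shown to database staff and cleaners who have no visit role, or why the plan should rule out using an uninvolved abstractor.

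A reader might infer more than the documents support:

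- *That masked abstraction is impossible in this trial.* The ID prevents it only under the plan as written, and the ID is not the only route to the arm.
- *That all delivery outcomes are compromised.* Most are numeric or leave little discretion.
- *That decisions to exclude CGM data are exposed and a neutral ID would protect them.* No exclusion procedure is described; the only sufficiency rule is a three-day threshold for repeating wear. The trace would also show the arm, because Section J has the intervention group wearing sensors continuously and controls wearing them in 10-day blocks.
- *That the numbering is itself a fault.* Section S can be read as sequential within group, and the prefix shows the arm on any reading.

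**Conclusion.** The point holds in limited form. The ID rule in Section S discloses the arm to everyone who handles a delivery record, and no supplied text offsets this. It bears on a short list of judgement-dependent outcomes under Aim 2. HbA1c, birth weight and gestational age are little affected. Neither the direction nor the size of any bias can be derived from the documents.

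The conclusion assumes that the two unavailable appendices contain no masking provision. The benefit of a change further assumes that at least some abstraction, entry or cleaning can be done by people without a visit role. The change is worth making because it costs little, not because harm has been shown.

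**What to change.** In Section S, replace the prefixed IDs with one arm-neutral sequential ID given at enrollment (for example GDM-001). Hold the allocation in a separate table with restricted access. State that delivery outcomes will be abstracted and locked under the neutral ID before allocation is merged. Where possible, use existing staff who did not fit sensors or download devices.

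The cost is a change of ID format, some reassignment of tasks, and a look-up of the arm when devices are issued. No new post is needed if uninvolved staff are available. The plan should say openly that masking will be partial, because visit coordinators know the arm and charts may contain CGM logs.
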